To investigate our hypothesis we will apply RNA-seq, rather than DNA microarrays, to generate transcriptional profiles, as this will enable quantitative assessment of both coding RNAs and ncRNAs. We will also use ATAC-seq to resolve the epigenetic landscape of immune cells in healthy elderly in the context of vaccine responses.

Approach:

1. *Blood transcriptomics by RNA-seq:* We will carry out RNA-seq of whole blood samples at baseline, day 1 and day 10. Samples collected from days 28 and 60 will be kept frozen for future studies. RNA-seq on purified cell subsets will be performed using purified cells from the five lowest and five highest responders for each vaccine. Sequencing will be performed at JAX-GM with an Illumina HiSeq2500.
2. *Blood epigenomics analysis by ATAC-seq:* We will analyze PBMCs, CD4+ T cells, monocytes, CD1cDCs and B cells (25×10^3 cells per assay). We are also developing assays with lower cell numbers to address the scarcity of some populations, and are encouraged by reports of single cell ATAC-seq [17]. We will generate a database describing the DNA accessibility landscape of major immune-cell subsets from elderly individuals at steady state. The data will also include the DNA accessibility landscape of monocytes, T and B cells analyzed at different time points following vaccination with the two pneumococcal vaccines. For these in-depth studies, we will select the five highest and five lowest responders for each vaccine.

Correlative analysis: We will correlate the increased levels of day 28 anti-pneumococcal antibodies as defined in Aim 1 with all the parameters collected in this aim. Parameters include: 1) cellular composition at baseline, day 1 and day 10 post-vaccination; 2) transcriptome analysis on blood and purified immune cell subsets at baseline, day 1 and day 10; 3) ATAC-seq data on PBMCs and purified cell subsets at the different time points and 4) pneumococcal colonization at baseline and at day 28. A detailed description of the statistical approaches is given below (see Integrative Data Analysis section).

1.3 Specific Aim 3

To examine the functional status of immune cells in the elderly stratified according to their pneumococcal vaccine responder status.

Hypothesis: We hypothesize that lack of *in vivo* response to PPSV23 and PCV13 depends on alterations to APCs, Tfh cells or B cells.

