Reproducibility of ATAC-seq datasets: To determine the feasibility of ATAC-seq for studying the epigenome of immune cells in the elderly, we conducted a pilot study in PBMCs (50,000 cells per experiment) of ten healthy young (20–30 yrs) and ten healthy old (>65 yrs) individuals. Each sample was run in triplicate to confirm reproducibility. ATAC-seq datasets were also generated in FACS-sorted B cells and in naïve and memory CD4+ and CD8+ T cells. We identified ATAC-seq peaks, i.e., open chromatin sites, in each of these PBMC samples. First, we confirmed that our identified ATAC-seq peaks are consistent with PBMC histone modification mark profiles generated by the Roadmap consortium, where ATAC-seq peaks are enriched in active marks (H3K9ac, H3K36me3, H3K4me1) and depleted in inactive marks (H3K9me3 and H3K27me3) (data not shown). Next, we calculated pairwise correlations between ATAC-seq datasets based on read count distribution across the whole genome and clustered the resulting correlation matrix (using hierarchical clustering algorithm) to identify similarities between ATAC-seq datasets globally.

Our analyses showed that ATAC-seq datasets are reproducible and capture cell-type-specific epigenetic landscapes. We found a good match between observed and expected open chromatin sites around cell-type-specific genes, e.g., the CD14 gene promoter had an open chromatin site in CD14+ monocytes (data not shown). We also identified cell-type-specific open chromatin sites in CD4+ and CD8+ cells by comparing memory and naïve ATAC-seq samples. We found that cell-type-specific open sites lose their specificity with aging both in CD4 and CD8 cells, with the change being more dramatic in CD8+ T cells. This preliminary study confirms that our ATAC-seq data generation and analysis workflow yields highly reproducible and high-quality ATAC-seq datasets from PBMCs and sorted cell populations.

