ATAC-seq identifies age-associated epigenetic changes in open chromatin sites: In our next set of ATAC-seq analyses, we sought to identify open chromatin sites remodeled with aging in PBMCs, i.e., open chromatin sites closing with age (“young specific”) or relatively closed chromatin sites opening with age (“old specific”). To do this we used an algorithm designed to capture differential sites from read count data based on negative binomial distributions; this allowed us to capture a total of ~20,000 differentially open chromatin sites (at 0.05 FDR cut-off, out of 100,000 consensus ATAC-seq peaks) between age groups, where ~11,000 were young specific and ~9000 old specific.

Among these differential sites, we found a remarkable genomic distribution bias between old-specific and young-specific open chromatin sites, whereby young-specific sites were mostly at promoters, whereas old-specific sites were enriched in intergenic and intronic regions. We confirmed that these differentially open chromatin sites separate age groups (i.e., elderly and young PBMCs) using the first two components of a principal component analysis (PCA) (data not shown). Among these differential open chromatin sites, we were further intrigued to find age-dependent closure of chromatin sites at the IL-7R promoter. This decline in chromatin accessibility correlated with a significant decrease in IL7R expression, as measured by RNA-seq. We also confirmed by flow cytometry that IL7R expression is decreased in elderly CD8+ T cells (data not shown). Moreover, among our “young-specific” differentially open chromatin sites, we identified ~60 promoter and intergenic ATAC-seq peaks targeting other genes in the IL7 signaling pathway, which is in agreement with the literature, as alterations in lymphocyte homeostasis related to the IL7/IL7R pathway have been reported in old mice and humans [83-87]. These analyses reveal that the epigenome of the IL7R signaling pathway significantly closes with aging, thereby

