uncovering a putative mechanism to explain the decreased ability of elderly individuals to deal with new antigenic challenges. They also further validate our approach using ATAC-seq to identify age-dependent differences in the epigenomes of healthy individuals. Here, we will extend these findings to determine whether vaccine responders and non-responders show differential expression and differential epigenetic profiles of immune-related molecular pathways. We will also analyze whether responders, in contrast to non-responders, reactivate their IL-7R pathways.

Modular interpretation of age-associated epigenetic changes. To systematically interpret the biological meaning of the remodeled open chromatin sites identified via ATAC-seq, we employed the transcriptional immune module analysis described in Fig. 1B, composed of gene sets that are coordinately expressed in PBMCs in a wide range of diseases (28 modules in total from 239 microarray profiles) [79-81, 88]. We developed and used this stable modular framework extensively to interpret immune signatures associated with diverse diseases and immune responses. We first identified putative (i.e., nearest) gene targets for ATAC-seq open chromatin sites. For each module, we then calculated the average log-fold change of read counts per gene between old and young samples for genes imputed to differential open chromatin sites. We next isolated modules whose chromatin landscape significantly changes with age, identifying 12 modules that are differentially open in samples from young individuals, including a module of T-cell regulators, and five modules that are differentially open in samples from elderly, including modules associated with neutrophil and platelet function and inflammation. We also investigated whether we can capture differences in module profiles of individual epigenomes when compared to population averages (i.e., all samples).

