We observed systematic and distinct differences in the relative openness of certain modules in samples from elderly versus young individuals, e.g., neutrophils vs. T-cell modules, which helps us to interpret the regulatory implications of epigenetic changes. Module-based functional analysis revealed that i) young-specific open chromatin sites mostly occur around promoters and are associated with modules related to T cell functions and ribosomal proteins; and ii) old-specific open chromatin sites mostly occur at intronic/intergenic sites and are associated with modules related to inflammation and neutrophil and platelet activity. Our modular analyses also helped us to identify outlier samples, including an old individual with a chromatin profile similar to samples from young individuals and vice versa. Modular analysis of immune epigenomes thus reinforced and enhanced our ATAC-seq analyses to provide greater insights into the immunogenomic profiles of elderly individuals. Here, it will be used to interpret epigenetic remodeling changes induced by vaccination in the elderly and to study whether responders and non-responders have different modular profiles before and after vaccination.

ATAC-seq datasets can be obtained from frozen samples. We next performed ATAC-seq on fresh and cryopreserved PBMCs from two different individuals. Our analyses revealed that fresh and frozen samples yield very similar genome-wide read-count profiles (data not shown), with only 44 peaks out of 75,365 total consensus open chromatin sites being different. These results confirm that ATAC-seq profiles can be obtained from frozen samples. This will enable us to retrospectively generate ATAC-seq datasets after vaccination responses are quantified, thereby significantly reducing experimental costs.

Differentially expressed non-coding RNAs in aging. Aging is associated with a complex transcriptional signature that includes changes to ncRNA profiles in addition to coding genes [89-96]. ncRNAs include small transcripts such as microRNAs and lncRNAs [1]. Although many

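### The only module statistic described for ATAC-seq averages genes already selected as differential in the same contrast; if the trial reuses it, module effects are exaggerated and modest coordinated shifts can be lost

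*Combined protocol and SAP*

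**What the plan says.** Section 2.1, Preliminary Studies III, describes an ATAC-seq pilot in "ten healthy young (20–30 yrs) and ten healthy old (>65 yrs) individuals". It first identifies about 20,000 "differentially open chromatin sites (at 0.05 FDR cut-off, out of 100,000 consensus ATAC-seq peaks) between age groups". Each open site is linked to its nearest gene. The module step, which uses "28 modules in total from 239 microarray profiles", does not average over all the genes in a set. In the protocol's words: "we then calculated the average log-fold change of read counts per gene between old and young samples for genes imputed to differential open chromatin sites". The text goes on to say "We next isolated modules whose chromatin landscape significantly changes with age" and reports 12 modules more open in the young and five more open in the old. It names no test for that statement.

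The same section brings modular analysis into the trial: "Here, it will be used to interpret epigenetic remodeling changes induced by vaccination in the elderly", and also to compare responders with non-responders before and after vaccination. For the in-depth ATAC-seq work, Section 1.2 states that "we will select the five highest and five lowest responders for each vaccine".

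Section 8.1 plans generalized linear mixed models by group and/or time, with Bonferroni or Benjamini-Hochberg (BH) correction. It mentions neither ATAC-seq nor modules. It does not say which genes or peaks enter a module summary, what the unit of analysis is, or what happens to a module with no called site.

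**The concern.** An average taken only over effects that have passed a significance filter in the same data overstates the effect, most of all in small groups. It also discards the module genes that did not pass. If 2 genes out of 100 change by 1.0 log2 and the rest do not, the all-gene mean is 2/100 = 0.02, while the mean over the changed genes is 1.0, the same as if all 100 had changed. Conversely, a small shift shared by every gene in a module can be invisible if no single site passes FDR, although a shared shift is what a module summary exists to detect.

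Modules are the stated means of interpreting the epigenetic vaccination and responder results. Distorted sizes, or silent modules, would pass straight into those interpretations.

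**Working it through.** The documents give no sample size, power or error rate for the module analysis, so there is no planned figure to reproduce. The check asks what the pilot rule would do at the trial's group sizes.

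**Inputs**
- Group sizes: 5 v 5 (Section 1.2) and 10 v 10 (pilot, Section 2.1).
- Site cut-off: BH at 0.05 with about 20,000 of 100,000 peaks called implies a raw p cut-off of 0.05 x 20,000/100,000 = 0.01. The trial's own cut-off would depend on how many sites pass.
- SD: 0.7 log2, from the RNA-seq power calculation in Section 8.2. Its use for ATAC-seq is an assumption.
- A two-sample t-test stands in for the pilot's negative binomial count model.

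**Step 1. Mean effect among selected sites.** The estimated difference is normal with mean equal to the true shift and SE = 0.7 x sqrt(2/n), that is 0.443 at n=5 and 0.313 at n=10. A site is kept if |t| exceeds 3.355 (8 df) or 2.878 (18 df). Simulated results:

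| Groups | True shift | Sites kept | Mean among kept | Ratio |
|---|---|---|---|---|
| 5 v 5 | 0.5 | 4.9% | 1.23 | 2.5 |
| 5 v 5 | 1.0 | 22% | 1.47 | 1.5 |
| 10 v 10 | 0.5 | 13% | 0.96 | 1.9 |
| 10 v 10 | 1.0 | 63% | 1.17 | 1.2 |

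Averaging all sites of the module returns the true shift in each case.

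**Step 2. Shifted modules with no called site (true shift 0.5, 5 v 5, BH 0.05).** The share depends on how many other sites change.
- Few other changes. With 28 modules x 100 sites, 8 modules shifted and within-module correlation 0.1, only 2-3% of shifted modules have any called site, so 97-98% are empty. With 200 genes per module, 3 modules shifted and 20,000 unchanged other sites, all are empty.
- Many other changes. With 20% of those 20,000 sites changed by 1.5 log2 up or down, 3-15% of shifted modules are empty; a separate check put the share with a called site at about 70% or more. The mean over called genes is then about 1.3 against a true 0.5. In the same setting 33-48% of unshifted modules have at least one called gene, with a mean absolute effect of about 1.0, against 0.03-0.12 over all their genes.

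**Step 3. A participant-level score over all sites.** For m sites with correlation r, SD of the score = 0.7 x sqrt(r + (1-r)/m). With m=100 and r=0.1 this is 0.7 x sqrt(0.109) = 0.231, so the SE of a 5 v 5 difference is 0.231 x sqrt(2/5) = 0.146. For a true shift of 0.5:
- BH over 28 modules with 8 shifted: about 50-57% detected at 5 v 5 and 97-98% at 10 v 10.
- Bonferroni 0.05/28 at 5 v 5: about 25-29%.
- BH with correlation 0.2 at 5 v 5: about 16-17%.

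The estimate stays unbiased and the type I error is about 5% per unshifted module.

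**The case against.** The best reply is that the averaging rule belongs to preliminary work on age, and that what is carried forward is modular analysis in general. No sentence says that the trial's averages will be restricted to differential sites. The same paragraph also describes comparing each individual's module profile with the average of all samples, with no such restriction stated, and that form suits the responder question at least as well. The stated purpose is interpretation, close to annotation. This stands in part: reuse of the restriction is an inference. But the restricted average is the only module statistic spelled out, and Section 8.1 offers nothing in its place.

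Three stronger readings are tempting and not supported.
- That the module average cannot be small whatever the truth. The averages are signed, so selected sites of opposite sign partly cancel.
- That at 5 v 5 the selected average is about 1 or more by construction. The figure 2.306 x 0.7 x sqrt(2/5) = 1.02 treats the SD as known. A t-test uses the sample SD, and with a true shift of 0.5 about 44% of sites passing p<0.05 lie below 1.02.
- That the method has a known, high false-positive rate because genes serve as replicates. The documents name no module test, so no such rate can be assigned to the plan.

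Two limits also stand. The results in Step 2 depend heavily on how many other sites change. And the calculations cover independent groups only; before-after vaccination contrasts are within person, so these figures do not give their size.

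**Conclusion.** The point holds conditionally. The only module statistic in the documents selects on the contrast it then estimates, the modular analysis is carried into comparisons of five versus five, and the analysis section gives no alternative. If the pilot rule is reused, a true shift of 0.5 log2 would appear as about 1.2 at 5 v 5. Large effects suffer less: about 1.5-fold at 5 v 5 and 1.2-fold at 10 v 10 for a true shift of 1.0. Loss of modestly shifted modules ranges from nearly all to a minority, according to how many sites pass FDR.

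These sizes rest on an SD of 0.7 log2 borrowed from RNA-seq, a site cut-off of p<0.01, a t-test in place of the count model, and assumed module sizes and correlations. The direction of the selection effect does not depend on those values. The change should be made, but this is an under-specified exploratory analysis and not a demonstrated error in trial results.

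**What to change.** In Sections 1.2 and 8.1, state that:
- for each participant and time point, a module score is computed as the mean normalised log accessibility over all consensus peaks assigned to the module's genes, whether or not they are individually differential;
- the scores are analysed in the mixed model already planned, with participant as the unit and terms for vaccine, time and responder group;
- BH-FDR is applied over the 28 modules;
- the list of individually differential sites is used only to annotate modules.

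The cost is a few sentences and modest analysis time, with no new samples or assays. Module effects will look smaller than in the pilot display. Power for small shifts at 5 v 5 stays limited when genes within a module are correlated (Step 3), and the text should say so.

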2.2 Significance

Pneumonia due to *Streptococcus pneumoniae* infection is a serious public health challenge among elderly populations. *S. pneumoniae* is the leading cause of community-acquired and in-hospital pneumonia in the United States (US) and globally, and a major cause of morbidity and mortality in the elderly. According to the CDC, an estimated 400,000 hospitalizations from pneumococcal pneumonia occur annually in the US; the case-fatality rate is 5–7% and may be >50% among elderly persons. Although pneumococcus-specific vaccines exist, elderly individuals display reduced responses for reasons that are as yet unclear, leaving many in this group highly vulnerable to infection and the consequences thereof. This project focuses on understanding the immune alterations associated with aging that affect responses to the two available *S. pneumoniae* vaccines, which differ respectively in composition and elicited host immune response. A better understanding of how elderly populations respond to these vaccines could be leveraged to improve overall efficacy and protection in elderly individuals—an outcome of significant public health relevance. Specifically, the proposed study would enable the identification of targets that could be modified to reactivate specific immune cells and/or pathways to improve vaccine response rates. Furthermore, the data generated would represent an important resource for future studies of elderly individuals with chronic diseases.

The declining ability of the aging immune system to combat infection is a major threat to the health, independence and survival of older adults (1-4). Cellular immunosenescence associated with a hyper-inflammatory state has been linked to many diseases common in the elderly, including infectious diseases (1, 5, 6). Beyond evidence of poor immune-cell responses with declines in naïve T cells, we know little about the mechanisms of immunosenescence (6-8).

3 STUDY DESIGN

This prospective, single-site, randomized, then open-label study is designed to develop a detailed transcriptional and epigenetic profile of the immune response to pneumococcal vaccination with conjugated and non-conjugated polysaccharide vaccines in the senescent immune system of older adults. This knowledge may lead to development of more effective vaccines through increased understanding of the effects of immunosenescence on mechanisms of immune response to pneumococcal vaccination in the elderly.

Forty (40) healthy adults ages 60 and older that have never received pneumococcal vaccination, will be randomized in a 1:1 ratio to receive Prevnar-13 (Pfizer), a conjugated 13-valent vaccine or Pneumovax 23 (Merck), a non-conjugated 23-valent vaccine. Following randomized assignment of vaccine, the study will be open-label.

The first six (6) study visits are planned to occur over 67 days at Days -7, 0, 1, 10, 28 (± 3 d) and 60 (± 5 d). Participants will provide blood samples for transcriptional, epigenetic and biological analyses pre- and post-vaccination.

One to two years after receiving the randomly-assigned vaccination, participants may opt to receive administration of a second pneumococcal vaccine with the vaccine that they did not receive by random assignment at Visit 2 (Day 0). This second vaccine will be provided at no charge to the participant. Administration of this vaccine will occur at an optional Visit 7 for participants who choose to receive the second vaccine and will be scheduled at the participant's convenience one-two years after receiving the first pneumococcal vaccine.

If the participant opts to receive the second vaccine within the study and attends optional Visit 7, blood samples for genomic and biologic analysis will be collected at the visit.

3.1 Characteristics of the Study Population

Number: 40
Age Range: 60 and older
Health Status: Healthy, as defined by eligibility criteria
Have never received pneumococcal vaccination
Duration of Participation: 6 visits* over approximately 70 days

*1 optional additional visit at 1-2 years for vaccination with the other vaccine not provided at Visit 2 (Pneumovax 23 / Prevnar 13, Prevnar 13/ Pneumovax 23). Optional Visit 7 to be scheduled at the convenience of the participant within 1-2 years for second vaccination with the other vaccine at no cost to the participant and for blood sample collection.

3.2 Sampling Plan

The study sample will be drawn from the population of healthy elderly in the catchment area of UConn Health in Farmington, CT.

4 SELECTION AND ENROLLMENT OF PARTICIPANTS

Forty (40) healthy men and women, ages 60 and older, from all ethnic backgrounds, that have never received pneumococcal vaccination will be recruited to this study over a two-year period. The National Health Interview Survey 2013 found that nationally, 40% of adults ages 65 and older have not received pneumococcal vaccination (1), which supports successful recruitment in this population. Recruiting participants aged 60 and up should enhance our recruitment efforts to ensure recruitment goals are met.

[name], the Principal Investigator of the clinical protocol, will utilize UConn Center on Aging recruitment resources for this project. The UConn Center on Aging Geriatric Recruitment & Community Outreach Core provides a centralized infrastructure for the recruitment of older research volunteers from the community. Over more than a decade [name], has managed this core. Such recruitment expertise, together with a

26,000-name database has permitted the successful completion of nearly 100 clinical studies involving older adults. Furthermore, under [name] leadership, the UConn Center on Aging has an established track record of recruiting more than 145 young and older adults each year for ongoing NIH-funded studies (PO1AG021600, R01AG048023) of the immune response to influenza vaccination in the elderly. Other recruitment methods will include recruitment flyers placed in local clinics, letters mailed to the Center on Aging database, use of broadcast email in the UConn Health system, and newspaper advertisements. Retention will be encouraged by planning visits at convenient times for the participants and by providing financial compensation for study participation.

Vulnerable Populations

Vulnerable populations will not be enrolled in this research study.

Collaborating Sites

All recruitment, enrollment, clinical data and sample collection will occur at the UConn Center on Aging located on the UConn Health campus in Farmington, CT under the direction of Clinical PI [name].

All transcriptional, epigenetic and biological analysis of samples will occur at the Jackson Laboratory for Genomic Medicine under the direction of Laboratory Analysis PI, [name].

